Study Phases	(1) Pre-screening : focus groups to determine details of the intervention
Screening	(2) Screening : screening for eligibility and obtaining consent, review medical record for HbA1C, obtain baseline Self-Care Inventory score
Study Treatment	(3) Intervention : review medical record for HbA1C, obtain Self-Care Inventory score
Follow-Up	(4) Follow-up : review medical record for HbA1C, obtain Self-Care Inventory score, complete satisfaction survey
Efficacy Evaluations	The primary efficacy endpoint will have two parts: the change in HbA1c between control and intervention groups between visit 1, 2 and 3.
Safety Evaluations	Adverse events are not anticipated in this study.
Statistical And Analytic Plan	Descriptive data analysis will include estimating means and standard deviations for continuous variables and counts and proportions of categorical variables for all aims. Two sample t-tests will be used to evaluate changes in HbA1c and SCI scores between the control and intervention groups and paired t-tests (or nonparametric methods if data is not normally distributed) will be used to compares the above changes within each group.
Data and Safety Monitoring Plan	The PI will monitor study progress, ensure the accuracy and security of the data, and ensure subject safety.

TABLE 1: SCHEDULE OF STUDY PROCEDURES

Study Phase	Screening	Control	Intervention	Follow-Up
Visit Number		1	2	3
Study Days		90 (+/- 30 days)	90 (+/- 30 days)	1
Informed Consent/Assent	X			
Review Inclusion/Exclusion Criteria	X			
Randomization	X			
Intake Questionnaire		X		
Height and Weight		X	X	X
HbA1c		X	X	X
SCI Questionnaire		X	X	X
Exit Questionnaire (Subjective Assessment of Intervention)				X

FIGURE 1: STUDY DIAGRAM

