2.1 Primary Objective (or Aim)

The primary objective of this study is to develop a text messaging intervention using MyDiaText and to determine whether such an intervention will decrease HbA1c in children 12 to 18 years. This will be divided into 2 parts:

- To determine whether this intervention will decrease HbA1c in children 12 to 18 years after 3 months +/- 1 month.
- To determine whether the effect of the intervention persists after an additional 3 months +/- 1 month of intervention.

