6.3.2 Efficacy Analysis

The primary analysis will include all subjects randomized at Visit 1 who have gotten HbA1c measurements at visit 2. The primary efficacy endpoint will be the change in SCI Score.

The first analysis will be change in SCI score from visit 1 to visit 2 comparing treatment and control groups. For this analysis we will use paired t-tests to test the null hypothesis of no difference in change in SCI scores at the two-sided $\alpha = 0.05$ level.

The secondary analysis will be the change in HbA1c between the intervention and control group from visit 1 to visit 2. For this analysis we will use two sample t-test to test the null hypothesis of no difference in the change in HbA1c at the two-sided $\alpha = 0.05$ level.

An additional secondary analysis will be the durability of the text messaging intervention from visit 2 to 3. SCI score and HbA1C will continue to be tracked to compare visit 1 to visit 3 and visit 2 to visit 3 at study conclusions.

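### The Visit 3 comparisons have no named test; the only stated method, an unadjusted t-test on change, gives up some precision and can be biased if loss after Visit 2 differs by arm

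*Combined protocol and SAP*

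**What the plan says.** Section 2.1 splits the primary HbA1c objective ("This will be divided into 2 parts"). The second part is "To determine whether the effect of the intervention persists after an additional 3 months +/- 1 month of intervention". The synopsis (Efficacy Evaluations) likewise describes the primary efficacy endpoint as "the change in HbA1c between control and intervention groups between visit 1, 2 and 3".

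Section 6.3.2 ranks the same comparison lower: "An additional secondary analysis will be the durability of the text messaging intervention from visit 2 to 3". On method it says only "SCI score and HbA1C will continue to be tracked to compare visit 1 to visit 3", and adds a Visit 2 to Visit 3 comparison in the same sentence. The one analysis set it gives is tied to Visit 2: "The primary analysis will include all subjects randomized at Visit 1 who have gotten HbA1c measurements at visit 2".

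The synopsis (Statistical And Analytic Plan) gives a general method without naming visits: "Two sample t-tests will be used to evaluate changes in HbA1c and SCI scores between the control and intervention groups". Section 6.3.2 repeats the two-sample t-test for HbA1c from Visit 1 to Visit 2 but names paired t-tests for SCI over that interval. No repeated-measures model, baseline adjustment or missing-data method appears anywhere.

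Section 4.5 lets the investigator discontinue subjects who do not adhere to treatment or keep visits. Section 4.5.1 asks for Visit 3 procedures at withdrawal. Where the subject withdraws by a STOP text, it provides a single e-mail carrying those procedures.

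**The concern.** Both Visit 3 contrasts (1 to 3 and 2 to 3) need a Visit 3 value. Under t-tests on change, a subject with Visits 1 and 2 only adds nothing to either, although the Visit 2 value helps predict the missing one.

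Two things are at stake:

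- **Precision.** A change score is less efficient than adjusting for baseline, and it cannot use a Visit 2 value where Visit 3 is missing.
- **Bias.** If subjects doing badly at Visit 2 are lost more in one arm, the Visit 3 comparison is distorted even though the data that would largely correct it have been collected.

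Arm-specific loss is plausible here. Only the intervention arm has texts to adhere to, so discontinuation for non-adherence to treatment (4.5) and withdrawal by STOP text (4.5.1) fall mainly on that arm. The two-weekly prize (7.1.1, 9.7.1) is also open to that arm only and could pull attendance the other way. Nobody is blinded (9.1.2). For SCI, collection at Visit 3 ends after two text reminders (3.2.4).

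**Working it through.** **Inputs from the documents.** Clinic HbA1c mean 9.11%, SD 2.26% and a target difference of 1 point (6.4); 200 subjects, 1:1 (3.3, 3.4.2); baseline HbA1c from 8% to below 14% (3.5.1); two-sided 0.05 (6.3.2).

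**Assumptions.** The documents give no between-visit correlations and no dropout rate. Correlations r12, r23, r13 are varied below. Missingness at Visit 3 is taken as 18%, the room between 164 and 200 (36/200), which leaves 82 of 100 per arm; some simulations use 30%. Restricting a normal(9.11, 2.26) to 8–14% gives a baseline SD s1 = 1.43.

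**Step 1: the plan's own figure.** Per arm, 2 × (1.960 + 0.842)² × 2.26² / 1² = 80.2, so 81. With the t distribution it is 82, and 2 × 82 = 164. The stated 164 is therefore reproduced as a parallel comparison of single HbA1c values. It uses no between-visit correlation and no dropout. The cross-over label in 6.4 does not reproduce it: a paired test needs 83 in total at correlation 0 and 43 at 0.5.

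**Step 2: precision at Visit 3, all correlations 0.7, 18% missing at random.** Here σ² = 5.108 and s1² = 2.045.

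- Residual variance given baseline: σ²(1 − r13²) = 5.108 × 0.51 = 2.605.
- Change-score variance: 2.605 + (1 − r13)² s1² = 2.605 + 0.09 × 2.045 = 2.789.
- Change-score t-test: √(2 × 2.789/82) = 0.261.
- Baseline-adjusted, subjects with Visit 3 only: √(2 × 2.605/82) = 0.252.
- Longitudinal model: the partial correlation of Visits 2 and 3 given baseline is (0.7 − 0.49)/0.51 = 0.412, squared 0.170. The SE is √(2 × 2.605 × [0.830/82 + 0.170/100]) = 0.248.

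Simulation under these assumptions gave 0.260, 0.252 and 0.249. A second simulation, with 10% missing at Visit 2 and 16–21% at Visit 3, gave 0.253, 0.245 and 0.239. The SD excess over the longitudinal model is 0.260/0.249 = 1.04 and 0.253/0.239 = 1.06. Baseline adjustment accounts for 0.008 of the 0.011 gap in the first and 0.008 of 0.014 in the second.

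**Step 3: lower correlations (0.5, 0.5, 0.4), 18% missing.** The same formulas give 0.350, 0.323 and 0.319, an excess of about 10%; power for 1 point is 0.81, 0.87 and 0.88. Without the baseline restriction the change-score SE rises to 0.387, an excess of 21%, and its power is 0.73 against 0.88. With complete Visit 3 data, Visit 2 adds nothing and the whole gain is baseline adjustment.

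**Step 4: when there is bias.** Selection on Visit 2 can distort a test only through the covariance of its outcome with Visit 2.

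- Change score: σ²r23 − r12r13(σ² − s1²) − r12s1². At 0.7 throughout this is 3.575 − 1.501 − 1.431 = 0.643. Without the baseline restriction and with r12 = r23 it is zero.
- Baseline-adjusted, subjects with Visit 3 only: σ²(r23 − r12r13) = 5.108 × 0.21 = 1.073, which is larger. Adding baseline to a single-visit test therefore does not cure this bias.

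Simulated mean Visit 3 estimates, true effect −0.5, r = 0.7, Monte Carlo SE about 0.01 (dependence is log-odds of loss per SD of Visit 2 HbA1c):

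| Dependence of loss on Visit 2 | Change t-test | Baseline-adjusted, Visit 3 only | Longitudinal | Change t-test minus longitudinal |
|---|---|---|---|---|
| Control arm only, 1.0 | −0.422 | −0.379 | −0.484 | 0.062 |
| Same, separate run | −0.449 | −0.406 | −0.507 | 0.058 |
| Control arm only, 0.5 | −0.478 | −0.459 | −0.508 | 0.030 |
| Both arms, 1.0 | −0.492 | −0.487 | −0.498 | 0.006 |

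Other assumed correlations, with 18–30% missing, widen the range. With dependence in the intervention arm only, the change-score bias ran from −0.06 to −0.40 points, in the direction of apparent benefit, and rejection under no effect ran from about 5% to 21%. The extreme came from correlations (0.6, 0.8, 0.5), a restricted baseline, 30% missing and the steepest dependence tried. With the same dependence in both arms, bias was nil under no effect and between about 0 and 0.12 points toward the null with a 1-point effect. The longitudinal estimate stayed within about 0.02 throughout.

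**The case against.** Several points on the other side are sound.

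- **The test is inferred.** A reader might infer that 6.3.2 prescribes a completers-only t-test at Visit 3. It does not. That follows from the synopsis and from the absence of any other rule. What is firm is that the method is unnamed and the only one on offer is the change-score t-test.
- **Visit 2 is not ignored.** A separate Visit 2 to Visit 3 comparison is planned. It does not recover subjects without Visit 3, however, because it needs that value too.
- **Dependence on Visit 2 is not enough for bias.** A reader might infer that the test is biased whenever attendance depends on Visit 2 HbA1c. The equal-dependence run contradicts this: −0.492 against −0.498. Material bias needs a mechanism that differs by arm; a shared one has an effect only where there is a treatment effect and change correlates with Visit 2.
- **Some values may be recovered.** Early-termination procedures (4.5.1) and HbA1c from routine clinic records (3.2.4) may supply Visit 3 data. The plan does not say whether an early-termination value counts as Visit 3, and an e-mail after a STOP text cannot itself yield an HbA1c.
- **The effects are modest and assumption-driven.** At r = 0.7 the bias of 0.06 is about a quarter of the estimate's SD (0.06/0.253). SCI was not simulated.

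It can also be argued that nothing in the documents suggests arm-specific loss. That does not stand, given sections 4.5 and 4.5.1.

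**Conclusion.** The point holds as a cheap improvement. The Visit 3 analysis is unnamed, and the one method stated is less efficient than a longitudinal model and exposed to arm-specific loss.

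At assumed correlations near 0.7 and about 18% missing, the cost is an SD about 4 to 6% larger, mostly from not adjusting for baseline. At (0.5, 0.5, 0.4) it is about 10% with the eligibility restriction on baseline. Bias is about 0.03 to 0.06 HbA1c points when Visit 2 drives loss in one arm only, up to 0.40 in the most adverse setting tried, and small when both arms behave alike. All of these rest on assumed correlations and missingness. None of them shows that the trial's result would be wrong, and the HbA1c figures do not transfer to SCI.

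Whether this comparison is part of the primary objective (2.1) or an additional secondary analysis (6.3.2) is unresolved. Those passages must be reconciled, but the comparison needs a defined analysis at either rank.

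**What to change.** In section 6.3.2:

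1. Analyse each outcome with one linear mixed model using all available Visit 1, 2 and 3 values, with baseline adjustment or a common baseline mean, arm-by-visit terms and unstructured covariance.
2. Report the Visit 2 contrast, the Visit 3 contrast and their difference from that model; the last two address persistence.
3. Define the Visit 3 analysis set and state how early-termination values map to Visit 3.
4. Keep the change-score t-tests as a sensitivity analysis and add one for data missing not at random.
5. Reconcile the rank of the Visit 3 comparison with section 2.1, and align the synopsis.

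The cost is about a paragraph of text and slightly more programming, with no new data collection. The main downside is reliance on missingness depending on observed values, which item 4 is there to probe.

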6.4 Sample Size and Power

The average HbA1c in adolescents at the CHOP Endocrinology and Diabetes clinic is 9.11% with a SD of 2.26%. Given this average HbA1c and its SD, a sample size of 164 subjects would be needed to observe a difference of 1% in mean HbA1c between groups at a

0.05 level of significance with 80% power in a cross-over study. We will aim to recruit up to 200 subjects out of over 1400 adolescents with T1DM seen at the CHOP Diabetes clinics for their routine care on a yearly basis.

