This phase will start at their next visit with their diabetes provider, which usually occurs after 3 months +/- 1 month. During this phase, control group will continue to not receive text messages, and intervention group will continue to receive text messages. HbA1c and diabetes treatment plan will be collected from the medical record. SCI will be completed at this time. All subjects will get \$10 for completing the second SCI. Invitation to fill out second SCI will be administered via text message. If second SCI is not filled out 7 days after this invitation, a reminder text message will be sent. If not filled out 7 days after reminder text message, a second reminder text message will be sent. No further reminders for that SCI will be sent.

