3.3 Allocation to Treatment Groups and Blinding

Half of the subjects will be randomized to the intervention and the other half will serve as controls. MyDiaText will randomly assign patients to treatment or control upon registration. Given the nature of the intervention, subjects will not be blinded. All study personnel and diabetes providers will not be blinded to current subject phase during the study, since unblinding should not result in bias in this study and it would be difficult to ensure that subjects do not tell their providers whether or not they are receiving text messages.

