6 STATISTICAL CONSIDERATIONS

6.1 Primary Endpoint

The primary endpoint will be the change in SCI score between Visit 1 and Visit 2 in control group as compared to intervention group

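### The only power statement is for a cross-over study, but the trial is parallel and tests change; no SD of change is given, and SCI, primary in Section 6, has no power basis

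*Combined protocol and SAP*

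**What the plan says.** Section 6.4 holds the only sample-size statement. Its inputs are cross-sectional: "The average HbA1c in adolescents at the CHOP Endocrinology and Diabetes clinic is 9.11% with a SD of 2.26" percent. From these it derives 164 subjects to detect a 1-point difference in mean HbA1c at the "0.05 level of significance with 80% power in a cross-over study". It then aims for up to 200.

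The design sections describe something else. Section 3.3: "Half of the subjects will be randomized to the intervention and the other half will serve as controls". Section 3.2.3 (Phase 2): "control group will continue to not receive text messages, and intervention group will continue to receive text messages". Section 3.5.1 limits entry to HbA1c of at least 8% and below 14%.

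On endpoints, Section 6.1 reads "The primary endpoint will be the change in SCI score between Visit 1 and Visit 2 in control group as compared to intervention group", and Section 6.2 lists change in HbA1c as secondary. The abstract, the synopsis (efficacy evaluations) and Section 2.1 treat HbA1c as primary.

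On analysis, Section 6.3.2 says of SCI "For this analysis we will use paired t-tests to test the null hypothesis of no difference in change in SCI scores", and of HbA1c "we will use two sample t-test to test the null hypothesis of no difference in the change in HbA1c". The synopsis gives two-sample tests for both between-group comparisons. Section 6.3.2 defines the analysis set by HbA1c: "The primary analysis will include all subjects randomized at Visit 1 who have gotten HbA1c measurements at visit 2".

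**The concern.** A power statement should match the design, the endpoint and the test. This one names a design the trial does not use. It takes its SD from HbA1c at a single time in all clinic adolescents, while the test uses change over about three months in patients selected for high HbA1c. It also concerns an endpoint that Section 6 ranks as secondary.

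The 80% is the only support offered for 164 and 200. As written, a reader cannot tell what HbA1c difference the change analysis can detect, or what SCI difference the trial can detect if SCI stays primary.

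Two neighbouring points bear on the SCI calculation. A paired t-test cannot compare two independently randomised arms. And SCI is returned after a text invitation with at most two reminders (Section 3.2.3), so the number with both SCI scores may differ from the number with a Visit 2 HbA1c.

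**Working it through.** **Inputs.** From Section 6.4: SD 2.26, difference 1, alpha 0.05, power 80%, 164 needed, 200 recruited. From Section 6.3.2: two-sided testing. From Section 3.3: 1:1 allocation. Not in the documents: SD of change, correlation between visits, dropout rate, any SCI quantity. Powers use the noncentral t distribution.

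**1. Reproducing 164.** The standardised difference is 1/2.26 = 0.442. A two-sided two-sample t-test needs 81.15 per arm, so 82 per arm and 164 in total. Power is 80.4% at 82 per arm, 83.9% at 90 and 87.6% at 100. The stated figure is exactly the two-arm parallel total for HbA1c at one visit.

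**2. What a cross-over would need.** The SD of the within-subject difference is 2.26 × √(2(1 − r)).

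| r | Subjects in total |
|---|---|
| 0 | 83 |
| 0.3 | 59 |
| 0.5 | 43 |
| 0.7 | 27 |

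No non-negative correlation gives 164.

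**3. Largest SD of change compatible with 80%.** This is 1 divided by the detectable standardised difference. Out of 200, 164 evaluable means 18% lost and 180 means 10% lost.

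| Evaluable per arm | Detectable standardised difference | Largest SD of change |
|---|---|---|
| 82 | 0.440 | 2.27 |
| 90 | 0.420 | 2.38 |
| 100 | 0.398 | 2.51 |

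**4. Power for a 1-point difference in change, by assumed SD of change.**

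| SD of change | 82 per arm | 90 per arm | 100 per arm |
|---|---|---|---|
| 2.00 | 89% | 92% | 94% |
| 2.26 | 80% | 84% | 88% |
| 2.40 | 76% | 79% | 83% |
| 2.50 | 72% | 76% | 80% |

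The detectable difference at 80% power is 1.06, 1.01 or 0.96 points if the SD is 2.40, and 1.10, 1.05 or 1.00 if it is 2.50.

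**5. Which correlation each SD implies.**

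*Equal SD of 2.26 at both visits, no entry restriction (assumption).* SD of change = 2.26 × √(2(1 − r)), so using 2.26 for change means taking r = 0.5.

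| r | SD of change | Power at 82 per arm | Power at 100 per arm |
|---|---|---|---|
| 0.3 | 2.67 | 66% | 75% |
| 0.5 | 2.26 | 80% | 88% |
| 0.7 | 1.75 | 95% | 98% |
| 0.8 | 1.43 | >99% | >99% |

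*Normal model with entry limited to 8 to below 14 (assumption).* Starting from mean 9.11 and SD 2.26, the enrolled baseline has mean 10.17 and SD 1.43. With r the correlation before restriction, the variance of change is (1 − r)² × 1.43² + 2.26² × (1 − r²).

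| r before restriction | r among enrolled | SD of change | Power at 82 / 90 / 100 per arm |
|---|---|---|---|
| 0.18 | 0.12 | 2.51 | 72 / 76 / 80% |
| 0.30 | 0.19 | 2.38 | 76 / 80 / 84% |
| 0.38 | 0.25 | 2.27 | 80 / 84 / 87% |
| 0.50 | 0.34 | 2.08 | 86 / 89 / 92% |
| 0.70 | 0.53 | 1.67 | 97 / 98 / 99% |

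Under this model 80% is reached at a correlation among enrolled patients of about 0.25, 0.19 or 0.12 with 82, 90 or 100 per arm.

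**6. SCI.** With a two-sample test, the detectable difference at 80% power is 0.44, 0.42 or 0.40 SDs of SCI change with 82, 90 or 100 per arm having both scores. The documents give no SCI SD, so this cannot be turned into points.

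**The case against.** The strongest reply is that this is a stray word. 164 is the correct parallel-group total, so deleting the cross-over label leaves the number intact. Under randomisation, a 1-point difference in follow-up means and a 1-point difference in change are the same effect; only the SD differs. The entry-restricted model reaches 80% at modest correlations, so the trial may well have the power it claims. If the restricted SD of 1.43 held at both visits (a further assumption), the SD of change at zero correlation would be 1.43 × √2 = 2.02, and power at 82 per arm would be about 88%.

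Much of this stands. There is no arithmetic error, and the HbA1c part alone would be a wording correction plus a sensitivity statement. The correlation thresholds depend on a normal model the plan does not supply. The shortfall in SCI returns is only a possibility: Section 3.2.3 pays $10 for the second SCI, and no loss rate can be derived. A detectable difference in SD units is also only a partial answer without an SCI SD.

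The reply does not reach the rest. Deleting one word does not supply an SD for the change test, settle which endpoint is primary, or give SCI any power basis.

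**Conclusion.** The point holds as a matter that should be fixed. The cross-over label contradicts the design, while the 164 is right for a parallel comparison of HbA1c at one visit. For the planned change test, 80% is not established. It requires an SD of change of at most 2.27, 2.38 or 2.51 at 82, 90 or 100 evaluable per arm, and the plan gives no such SD. Power could fall on either side of 80%, so this is no claim that 164 or 200 is too small.

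The weightier part is the endpoint. Section 6 makes SCI primary without an effect size, SD or power, against the abstract, synopsis and Section 2.1, and it names a paired test for a comparison between arms. Confidence intervals would keep the results interpretable; the gap is in the planning basis.

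The reproduction of 164 and the SD limits use the plan's 1-point difference and two-sided alpha with the stated per-arm numbers. Everything expressed through a correlation rests on the assumptions labelled above.

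**What to change.** Keep enrolment at 200 and make four changes.

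- **Design.** In Section 6.4 replace the cross-over wording with a two-arm parallel-group design, 82 per arm, two-sided alpha. Relabel the Table 1 columns, which head Visit 1 as control and Visit 2 as intervention.
- **Endpoint and test.** Name one primary endpoint in the abstract, synopsis, Section 2.1 and Section 6. Use a two-sample test for the between-arm comparison of SCI change.
- **HbA1c power.** Restate power, or the detectable difference, for the Visit 1 to Visit 2 change by evaluable number per arm. Claim 80% for 1 point only if the SD of change is within the limit for that number; otherwise report the larger detectable difference. Take the SD from roughly three-month changes in existing clinic data on eligible adolescents if available. If not, show the range over assumed correlations and say whether each is before or after the entry restriction.
- **SCI power.** If SCI stays primary, state 0.44, 0.42 or 0.40 SDs of SCI change at 82, 90 or 100 per arm, counting subjects with both SCI scores.

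The cost is wording, mainly in Section 6 and Table 1, with no extra patients or visits. Section 5.3.1 says HbA1c is checked every 3 months in routine care, so consecutive values should exist. Access and approval to use them are not documented, but the correlation range needs no data. The stated power, or the 1-point detectable difference, may become less favourable.
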